Visits take place at baseline (T0), after two (T1), four (T2) and six months (T3). Each visit includes a spirometry (EasyOne Pro, ndd Medizintechnik AG, Zurich, Switzerland), measurement of diffusion capacity (EasyOne Pro, ndd Medizintechnik AG, Zurich, Switzerland), exhaled nitric oxide (NIOX MINO®, Aerocrine AB, Sweden) and carbon monoxide (piCO⁺ Smokerlyzer, Bedfont Scientific Ltd., Kent, UK) measurements. To detect false device applications, each patient is asked to demonstrate the inhalation technique with all prescribed devices to the investigator using a placebo device (to avoid overdosing). Moreover, participants have to fill out the COPD Assessment Test (CAT)[41], the Asthma Control Test (ACT)[42], the St. George’s Respiratory Questionnaire (SGRQ) and the Short Form (SF)-36[43, 44] to assess quality of life at baseline, after two, four and six months. To assess patients’ beliefs about the necessity of the prescribed medication and their concern about the potential adverse consequences of taking it, the Beliefs about medicines Questionnaire (BMQ) is used at baseline[45, 46]. During these visits we also obtain information about exacerbation since the previous visit.

RANDOMIZATION

After having given written informed consent eligible subjects are randomly assigned either to the intervention or to the control group. The intervention group is provided with an acoustic reminder for inhalation and receives support calls when the medication is not taken as prescribed while the control group receive no further support regarding the adherence. A randomization list with study group allocation is generated using R (RStudio®, Boston, USA). Randomization procedure is provided in block size of two. Therefore, examinations between study groups are sequent. This reduces the risk of a season effect between study groups. The patients are not aware of which group they have been randomized to (single-blinded).

CLINICAL INTERVENTIONS

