Currently, no monitoring devices exist that were specifically developed for monitoring the adherence of the newly introduced inhalation-device Ellipta®. To assess adherence in patients undergoing treatment with Ellipta® a Smartinhaler with a placebo-device is handed out and patients are instructed to trigger a puff of the placebo every time when they inhale their active treatment. This procedure allows an indirect recording of date and time actuation of the Ellipta® inhaler.

For inhalation with powder capsules (Breezhaler and HandiHaler), POEMS are used. The capsules are pre-filled for the following 2 weeks with a patient's individualized prescription plan (mostly one time daily inhalation of capsule contents). The multidose punch cards are filled manually by a pharmacist. The participants with Breezhaler and HandiHaler will receive one multidose punch card for every 2 weeks. Every time the patients break a loop for taking the capsules, date and time are recorded on a microchip, which can be read when the patients bring back the empty punch card.

DATA COLLECTION AND OUTCOME MEASURES

The primary outcome of this study is “time to next asthma or COPD exacerbation”, defined as acute-onset worsening of the patient's condition beyond day-to-day variations requiring interaction with a health care provider[48], which may occur during the index exacerbation or follow-up. Data collections about this outcome are assessed after two, four and six months (number of exacerbations since last visit with exact period of exacerbation and number of exacerbation with hospitalization). If patients are not able to give information about the time of exacerbation, treating physician is contacted.

Sociodemographic variables such as gender, civil status, age, education level and employment status are obtained by a generic questionnaire at the baseline visit. Furthermore, body mass index (BMI), smoking status, as well as pack years (py) are assessed during this visit. In addition, disease-related questions such as allergies,

comorbidities, current medication and number of exacerbations in the previous twelve months are recorded including hospitalizations and emergency department attendance.

This project focuses on the implementation of a prescribed dosing regimen. Objective adherence will be analyzed according to the following widely used definitions[49]:

- Taking adherence: (Number of puffs inhaled during 24h/number of puffs prescribed during 24h) x 100.

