Statistical analyses, including descriptive statistic and survival analyses, are done using the software R (RStudio®, Boston, USA) and SPSS (IBM Corporation, Armonk, USA). Statistical significance is set at the 5% level. Time to next exacerbation is compared using the Kaplan-Meier method and Cox proportional hazard model. Results will be reported as HR (hazard ratio) with corresponding 95% confidence interval (CI) and p-value. A hazard ratio smaller than one is expected. This means that the intervention group will have a smaller risk for exacerbations. Associations between time to between exacerbation and independent predictors will be analyzed (taking adherence, timing adherence and gaps without

inhalation). Comparisons of secondary parameters are done using t-tests or chi-square-tests (or their nonparametric equivalents if continuous data are not normally distributed).

HANDLING OF MISSING DATA AND DROP OUTS

Patients will be rated as drop out when they will be excluded from the study at their request or if they will be no longer able to participate in the study until the final visit at six months. Patients, who will not be able to undergo all clinical examination during the follow-up visits, will remain in the study. Multiple imputation methods will be used to impute missing data with less than 25% missing values, which is typically more efficient than complete cases analysis when covariates have missing values[56].

ETHICS AND DISSEMINATION

This study is conducted according to the Helsinki Declaration and according to the good clinical practice guidelines. The study participation of the patients is voluntary and can be revoked at any time without specification of reasons and will have no disadvantages for their future medical care. The study was approved by the Ethics Committee of Nordwest- and Zentralschweiz (registry number: EK- 269/13) and was registered in the <https://clinicaltrials.gov/trials> database (NCT02386722). The results of this study will be disseminated via seminar and conference presentations and in academic peer reviewed journals.

DATA SECURITY/DISCLOSURE OF ORIGINAL DOCUMENTS

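### No method is stated once 25% or more of a secondary outcome or adherence measure is missing, although earlier-visit data could be used

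*Combined protocol and SAP*

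**What the plan says.** Handling of missing data and drop outs sets the rule: "Multiple imputation methods will be used to impute missing data with less than 25% missing values". Its reason is that imputation is a method "which is typically more efficient than complete cases analysis when covariates have missing values". The same section provides for gaps in visit data: "Patients, who will not be able to undergo all clinical examination during the follow-up visits, will remain in the study". It does not say whether the 25% is counted per variable, per patient or over the whole data set. It also does not say what is done at or above 25%, what the imputation model contains, or what missingness mechanism is assumed, and it gives no sensitivity analysis.

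Statistical analysis gives the methods to which the rule applies. For the primary outcome: "Time to next exacerbation is compared using the Kaplan-Meier method and Cox proportional hazard model", with no adjustment covariates named. For the rest: "Comparisons of secondary parameters are done using t-tests or chi-square-tests", or nonparametric equivalents. Time to exacerbation is also to be related to taking adherence, timing adherence and gaps.

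The data are longitudinal. Study design and procedures has the questionnaires completed "to assess quality of life at baseline, after two, four and six months", and Data collection and outcome measures puts lung function on the same schedule. Under Measurement of objective adherence, data for capsule inhalers sit on a microchip "which can be read when the patients bring back the empty punch card".

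**The concern.** The rule runs against its own reason. If imputation is chosen because it recovers information that complete cases lose, there is more to recover as the missing fraction rises, yet the plan's commitment ends at 25%. Beyond that point the only procedures named are two-sample tests, and these have no place for a patient's earlier values. The realised fraction is known only once data are in, so the choice of method for the sparsest variables is left until then.

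At stake are the month-6 comparisons of quality of life and lung function, and the models relating adherence to exacerbation. Unreturned punch cards are a plausible source of missing adherence data. The reason given also refers to missing covariates, whereas the visit-based gaps that the plan foresees fall largely in outcomes.

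**Working it through.** The 25% limit has no derivation to reproduce, and the plan's sample size and power do not depend on it. The documents give no expected missingness by variable and no variances, so steps 2 to 4 are illustrations with assumed inputs.

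**1. Where the limit bites** (taken as per variable; N from Calculation of sample size)

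- 0.25 × 154 = 38.5. Imputation applies with up to 38 missing (24.7%) and stops at 39 (25.3%).
- Study design and procedures gives 169 participants: 0.25 × 169 = 42.25, so it stops at 43.
- Planned dropout is 14/154 = 9.1%. A further 39 − 14 = 25 patients would have to lack the variable.

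**2. Efficiency, the plan's own criterion**

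Assume a random intercept SD of 0.8 and residual SD of 0.6. The total variance is 0.64 + 0.36 = 1, and any two visits correlate at ρ = 0.64. The squared multiple correlation of T3 on T0, T1 and T2 is R² = 3ρ²/(1 + 2ρ) = 1.2288/2.28 = 0.539.

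With a fraction f lost completely at random, the large-sample variance of an arm mean is σ²/[n(1 − f)] for complete cases. With imputation from earlier visits it is (σ²/n)[1 + (1 − R²)f/(1 − f)]. The ratio, imputation to complete cases, is 1 − R²f.

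| f | variance ratio | SE ratio |
|---|---|---|
| 0.10 | 0.946 | 0.973 |
| 0.24 | 0.871 | 0.933 |
| 0.26 | 0.860 | 0.927 |
| 0.40 | 0.784 | 0.886 |

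Simulation with 77 per arm agrees: SE 0.164 for imputation against 0.168 for complete cases at 10% (ratio 0.976), and 0.190 against 0.214 at 40% (ratio 0.888). The gain rises smoothly with f, with no break at 25%.

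**3. Bias in the month-6 comparison**

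Same variances, 77 per arm, no true effect, 30% missing at T3, with loss depending on the observed T2 score:

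| Loss mechanism | Complete-case bias (SD) | Using T0–T2 |
|---|---|---|
| Random, or same pattern in both arms | about 0 | about 0 |
| Same direction, log-odds slope 1 against 0.5 | about 0.07 | – |
| One arm only | about 0.17 | about 0 |
| Opposite directions, odds ratio 1.65 per SD | 0.18 | – |
| Opposite directions, odds ratio about 2.7 per SD | about 0.33 | about 0 |

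A dash means that the imputation result was not tabulated for that case. A milder version of the one-arm case gave 0.10, 0.11, 0.12 and 0.17 SD at 24%, 26%, 30% and 40% missing, so bias is nearly the same on either side of the limit.

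**4. Limits of the remedy, and the adherence models**

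A separate illustration used outcome SD 1, baseline correlation 0.6 and true difference 0.30, with loss depending on the unobserved outcome differently by arm. Complete-case bias was 0.41 at 24% and 0.44 at 26%; imputation bias was 0.28 and 0.29. Imputation reduces this bias but does not remove it.

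For a Cox covariate with an assumed log hazard ratio of −0.5 per SD, complete-case bias stayed within 0.012 of zero if missingness was random or depended on the covariate only. If missingness depended jointly on covariate and event, bias was −0.23 at 24% and −0.27 at 26%.

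**The case against.** Four points can fairly be made against the concern.

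- **The fallback is not written down.** A reader might infer that the plan uses complete cases above 25%. It does not say so: complete-case analysis appears only as the comparator for efficiency. Dropping the variable or reporting it descriptively are equally open. This stands. The defect is an unstated method, and the bias figures apply only if the test is run on observed values.
- **More missing data need not mean more bias.** A reader might infer that imputation is withdrawn exactly where complete cases are most biased. Bias depends on the mechanism as well as the fraction. It was about zero even at 40% when loss was random or alike in both arms, and under missing-not-at-random loss imputation is biased too. This also stands.
- **The limit may never be reached, and the large figure is an extreme.** Planned dropout is well short of 25%, and nothing in the documents indicates dropout in opposite directions by arm. Only intervention patients receive reminders, calls and adherence feedback, so loss that differs by arm is conceivable, but that is a conjecture. Hence a range is given.
- **Earlier visits might already be used, and a mixed model is a separate preference.** Below 25% the undescribed imputation model could include them, so it cannot be said that they go unused throughout. At or above 25%, no named method uses them. Imputation followed by a t-test would also serve; the mixed model is preferred because it uses all visits and makes the cut-off irrelevant for repeated continuous outcomes.

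Caution about relying on imputation when much is missing is reasonable. The answer is to report the fraction missing and test the assumptions, since complete-case analysis rests on assumptions as well.

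**Conclusion.** The concern holds in a limited form. At 39 or more of 154 missing the plan states no method, its own reason for imputing is stronger there than below the limit, and a method using data already collected is available. The general gain is precision: under the assumed variances, an SE about 7% smaller near 25% missing and 11% smaller at 40%, for loss completely at random. Avoided bias is conditional, ranging from about 0 to about 0.33 SD at 30% missing according to mechanism, and only if observed values alone would have been analysed.

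The reach is confined to secondary outcomes such as quality of life and lung function, and to the adherence-predictor models. The primary arm comparison names no covariates and is essentially untouched. This is an improvement worth making, not a threat to the trial's main conclusion. It rests on reading the 25% as per variable and on assumed variances and mechanisms.

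**What to change.** - Analyse continuous outcomes at T1 to T3 with a linear mixed model using all available visits and the baseline value, with the month-6 difference between arms as the contrast.
- Drop the 25% cut-off for missing covariates and adherence. Impute with arm, event indicator, cumulative hazard and earlier-visit values as predictors, and state the missing-at-random assumption.
- Report the fraction missing beside each result, with complete-case and missing-not-at-random sensitivity analyses. Complete cases alone do not address the latter.

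The cost is a few lines of text and modest extra programming, with no new data. Intervals will be wider for variables with much missing data, which reflects the information actually available.
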